9. TRIAL PROCEDURES

9.1. Schedule of assessments

Assessment		Screening	Day 0	48 hours (or maternal discharge if sooner)	Neonatal Discharge	3 months ±7 days
Eligibility check		x	х			
Valid informed consent			Verbal	x ¹		
Randomisation			х			
Co-primary Outcomes	Anal sphincter injury		x			
	Caesarean		х			
Neonatal Composite & Components					x	
Assessment of Adverse Events				x	x	x
Process Outcomes	Use of ultrasound to diagnose position before rotation	x				
	Position of fetal head before rotation	x				
	Position of fetal head at birth		х			
	Position of the ventouse cup		x			
	Forceps marks on the baby (diagrams)		x			
	Adherence to key steps of the manual rotation process		x			
	Adherence to standardised assessment of the primary outcome		x			
Maternal	Vaginal birth after successful rotation with the first instrument		x			
	Change from rotational ventouse to rotational forceps		x			
	Severe/complex 2 nd degree vaginal/cervical tears		x			
	Breastfeeding (UK Infant Feeding Survey)			x		x
	Estimated blood loss			x		
	Need for red blood cell transfusion (or use of cell salvage)			x		
	Urinary Incontinence ICIQ Fecal Incontinence Quality					x x
Maternal Experience	of Life Scale Childbirth Experience Questionnaire (CEQ)			x		x
	Client Satisfaction Questionnaire (CliSQ)			x		x
Maternal PTSD symptoms	CITY Birth Trauma Scale					x

¹ Where participants do not give written consent routine clinical data will be collected on the Day 0, 48 Hour Follow Up and Neonatal CRFs only

Any paper CRFs should be submitted upon completion. Quality of life questionnaires may be emailed directly to participants for completion if they are not in hospital at the assessment timepoint; or may be completed over the phone with the research midwife.

9.2. Discontinuation of Trial Intervention

Participants should be made aware at the beginning during the consent process that they can freely discontinue their participation in the trial at any time without giving a reason. The details of changes of levels in participation within the trial (date, reason and category of status change) should be clearly documented in the source documents and captured on the Trial Withdrawal CRF.

Types of discontinuation are:

- Participant would like to withdraw from the trial but has agreed to attend follow-up visit and/or provide follow-up data for use in the trial analysis
- Participant would like to withdraw from the trial and does not wish to attend follow-up visits but is willing to be followed up at standard clinic visits (the participant has agreed that follow-up data can be collected at standard clinic visits and used in the trial analysis)
- Participant is not willing to be followed up for trial purposes at any further visits (the participant has agreed that any data collected prior to the withdrawal of consent can be used in the trial analysis)
- Participant wishes to withdraw and that none of their data collected to date be used for any trial purposes

Women who have not given consent will not be considered study participants. Anonymised data used at randomisation after verbal consent is given will be retained and could inform our understanding of the (basic) characteristics of women eligible who decline to participate, alongside the formal qualitative study: we will talk to a small number of women who decline to help understand in more detail why they decline.

Clinical data collected on women eligible (for example, standardised assessments of perineal tears) who provided verbal consent but declined to provide full written consent will remain as part of each individual's medical records but neither used for completion of any additional study documentation nor uploaded to the study database.

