5.3 Consent process

Postnatally (prior to discharge, usually within 24-48 hours), a full patient information sheet will be provided to these women who verbally consented, and written consent will be sought for the use of data already collected, for participation in follow-up, and for participation in qualitative work (in the pilot) if applicable.

- Following informed verbal consent there will be automated telephone randomisation. Telephone randomisation has been shown to be efficient and pragmatic in several intrapartum trials in our experience. We have kept the number of minimisation factors to the minimum to enable an efficient and rapid randomisation process. Most of the clinicians in our national survey perform rotational deliveries in theatre which will increase the chances of recruiting – there is, in such deliveries, more time and more personnel available compared to deliveries in the labour ward room. In addition to telephone randomisation, we could also offer the option to randomise the patient via an internet-based portal. We have accounted for any missed opportunities in the very conservative estimates of recruitment rates (on average six women per site per month). Using an adaptive approach, we will monitor the randomisation process during the pilot period and amend as necessary based on the process evaluation.
- It will be the responsibility of the Principal Investigator (PI) to obtain written informed consent for each participant. This task can be delegated by the PI to other members of the local research team, most likely a Research Midwife, if local practice allows and this responsibility has been documented in the site signature and delegation log.

- Where a patient gives verbal consent and is randomised but does not give written consent anonymised data will be collected on the Day 0, 48 Hour Follow Up and Neonatal CRFs only (please see Section 5.3 for further details)
- Additional consent will be taken in the pilot for the **qualitative work** with women, partners, and healthcare professionals: interviews and audio recordings etc.

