At each encounter, the participant's **willingness to continue** in the trial will be ascertained and documented in the medical notes. Throughout the trial, the participant will have the opportunity to ask questions about the trial. Any new information that may be relevant to the participant's continued participation will be provided. Where new information becomes available which may affect the participants' decision to continue, participants will be given time to consider and if happy to continue, they will be re-consented. Re-consent will be documented in the medical notes. The participant's right to withdraw from the trial will remain.

Where participants do not give written consent after randomisation anonymous clinical data will be collected on the Day 0, 48 Hour Follow Up and Neonatal CRFs to allow monitoring of safety. The provision of anonymous data is in line with General Data Protection Regulations (2018) and Common Law. Participants who do not give written consent will not be asked to complete questionnaires give any follow up information.

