5.4. Discharge / transfer to another hospital prior to written consent

It is expected that consent will be sought for all participants prior to discharge/transfer to another hospital.

In the rare instances where consent is not sought prior to discharge/transfer, the following should occur:

The Research Midwife (RM), or other designated member of the research team at site, will call the participants within 5 working days of randomisation to inform them and/or their family of the participant's involvement in the trial and provide details of the trial.

Once the telephone call has been completed, the RM, or other designated member of the research team at site, will post/email within 5 working days as applicable:

- Participant covering letter to home/email address
- Participant information sheet and consent form to home/email address

The covering letter will confirm that the participant has 4 weeks from the date of the letter to return the consent form confirming whether they would like to continue participation in in the trial.

If no response is received within 2 weeks (14 days), the RM, or other designated member of the research team at site will make a follow up call to the participant to check that they have received the information and request that the consent form be returned within 5 working days if they would like to continue participation in the trial. Written information and a consent form will be re-sent if the site team member is unable to contact the participant, or information has not been received.

If no response is received within 4 weeks (28 days), the participant's data will not be included within the trial as confirmed in the telephone conversation/covering letter. Consent is being sought in this scenario for the disclosure of confidential information in order to avoid a breach of the common law duty of confidentiality. If we find that consent in this scenario is not practicable and results in informative missing data (e.g. linked to severity of condition or duration of hospital stay) a future Section 251 application may be made for future participants.

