8. OUTCOME MEASURES AND TRIAL PROCEDURES

8.1. Pilot Stage of Trial Outcomes

Trial Outcomes

All the main trial outcomes will be collected in the pilot stage and will be included in the analysis.

Progression Criteria

The decision to continue to a full trial will be decided by pre-defined independent stop-go criteria (red, amber, green (RAG) traffic lights) and supplemented with the findings from the pilot qualitative process evaluation.

8.1.1	Table for the stop-go	criteria for progressio	n from the pilot phase to full ti	rial
0.1.1	Table for the stop Bo			

Pilot (9 months)	Red	Amber	Green
Trial recruitment	<80%	80-99%	≥100%
Recruitment rate/ site/ month	<5	5-6	>6
Number of sites opened (staggered)	<9	9-11	12
Total number of participants recruited	<350	350-432	≥437
Adherence of women to randomised procedure	<90%	90-95%	>95%
Follow-up of women randomised – 3 months	<80%	80-95%	>95%
Written consent not received for women randomised	>10%	5-10%	<5%

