We have calculated sample sizes for the CS outcome with varying non-inferiority (NI) margins. The table below provides the sample size required based on a 12% or a 15% control group (forceps/ventouse) CS rates, at 90% power, and a one-sided 2.5% alpha, with the knowledge that we are aiming for a total sample size of 5200, assuming negligible loss to follow-up for this outcome as mode of delivery is captured in hospital notes.

Control rate	NI margin	Total sample size
12%	2.9%	5278
	3.0%	4932
	3.5%	3624
	4.0%	2774
15%	3.0%	5956
	3.2%	5234
	3.5%	4376
	4.0%	3350

Therefore, the planned study of 5,200 women would be able to identify with more than 90% power a non-inferiority margin of 3.5% if the control group rate is 15%.

Both of our PPI co-applicants have discussed the issue of the non-inferiority margin extensively with women through their networks and social media. Despite the large range in experiences, a common theme is that the actual non-inferiority margin does not matter much to women; what matters is the provision of adequate information about the interventions and the research, a focus of our qualitative research and pilot.

We have therefore selected 3.5% as the non-inferiority margin, which represents a relative risk increase of CS of 23% (from 15% to 18.5%), noting that the originally proposed margin of 3% represented a relative risk increase of 20% (from 15% to 18%).

Other outcomes: The proposed sample size would also have 90% power in detecting an absolute risk difference in serious neonatal morbidity and trauma composite of 1.65% (assuming risks of 4% and 2.35% in the two groups). However, we consider the neonatal composite an important secondary outcome to provide a safety signal, and we have powered ROTATE for maternal outcomes as per the commissioning brief. This sample size of 5,200 is therefore justified for a trial with the potential to change obstetric practice and improve outcomes that truly matter for mothers, babies, and their families.

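### The protocol gives conflicting rules on keeping Day 0 outcome data for randomised women who do not give written consent, and two of those rules make inclusion depend on events after birth

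*Protocol*

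**What the plan says.** Three places keep the data.

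- Section 5.3 (Consent process): where a randomised woman "does not give written consent anonymised data will be collected on the Day 0, 48 Hour Follow Up and Neonatal CRFs only".
- Section 5.3 (General Provisions) repeats the rule for the same three forms. It is the only place that gives a purpose, and that purpose is limited to safety: "Neonatal CRFs to allow monitoring of safety".
- Section 9.1, footnote 1 to the schedule: "Where participants do not give written consent routine clinical data will be collected on the Day 0, 48 Hour Follow Up and Neonatal CRFs only".

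Two places discard them.

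- Section 9.2, last two paragraphs: women who have not consented are not study participants. Anonymised randomisation data are retained. For women who gave verbal but not written consent, clinical data stay in the medical record and are "neither used for completion of any additional study documentation nor uploaded to the study database". The example given is the perineal-tear assessment, which is the superiority outcome.
- Section 5.4: if a woman was discharged or transferred before consent was sought and has not replied within 28 days, "the participant's data will not be included within the trial as confirmed in the telephone conversation/covering letter".

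Three other statements bear on this. Section 14.2 analyses all participants as randomised. Section 14.1 allows about 4% loss for tears, and for caesarean section it plans "assuming negligible loss to follow-up for this outcome as mode of delivery is captured in hospital notes". The pilot table in 8.1.1 has a row headed "Written consent not received for women randomised": green below 5%, amber 5-10%, red above 10%.

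**The concern.** The two sets of rules cannot both be followed for a woman who verbally consents, is randomised, gives birth and then declines to sign. Under 5.3 and 9.1 her Day 0 CRF is completed. Under 9.2 her outcome may not go onto study documents or into the database. Two sites could each follow the protocol and treat her in opposite ways.

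Timing makes this more than an editorial matter. Section 8.2.1 records both co-primary outcomes on the day of birth. Sections 5.3 and 6.1 seek written consent afterwards, usually within 24 to 48 hours, and section 6.4 confirms that there is no blinding. By then the woman knows how she gave birth, whether she had a severe tear and which method was used. If refusal or non-response is related to those facts, excluding her selects on outcome within arm. Section 5.4 itself recognises that the missing data could be informative.

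Section 9.2 also takes non-signers out of the class of participants, so the intention-to-treat set in 14.2, which is defined on participants, shrinks after randomisation.

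**Working it through.** **1. The plan's own figures.** Inputs are from 14.1.

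- Superiority: 6% vs 4%, two-sided 5%, 90% power. With pooled variance under the null, n per arm = [1.96·√(2×0.05×0.95) + 1.2816·√(0.06×0.94 + 0.04×0.96)]² / 0.02² = 2,494, so 4,988 in total, as stated. 4,988/0.96 = 5,196, rounded in the plan to 5,200.
- Non-inferiority: 15% in both arms, margin 3.5 points, one-sided 2.5%. n per arm = (1.96 + 1.2816)² × 2×0.15×0.85 / 0.035² = 2,188, so 4,376 in total, as stated. All eight rows of the caesarean table reproduce.

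No stated sample-size figure is wrong.

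**2. Power if non-signers are removed.** Same formulas, solved for power, with no other loss except in the second row.

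| Loss | N analysed | Superiority | Non-inferiority (15%, 3.5 points) |
|---|---|---|---|
| None | 5,200 | 91.2% | 94.2% |
| 4% (planned for tears) | 4,992 | 90.0% | 93.4% |
| 5% non-consent (260 women) | 4,940 | 89.7% | 93.1% |
| 10% non-consent (520 women) | 4,680 | 88.1% | 91.8% |

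With a further 4% lost for other reasons, 10% non-consent leaves 4,493 women, with power of 86.8% and 90.7%.

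**3. Selection.** The protocol gives no refusal rates, so these are assumptions: non-consent is 5% in general and 20% among women with the event, in both arms or in one arm only. Overall loss is then 5.3% to 7.5%. The observed risk is p(1 − w₁) / [p(1 − w₁) + (1 − p)(1 − w₀)], where w₁ and w₀ are the non-consent rates with and without the event. For p = 5%, w₁ = 20%, w₀ = 5%: 0.0400/(0.0400 + 0.9025) = 4.24%.

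| Outcome, true risk (manual vs instrumental) | Excess non-consent in | Observed | Difference, points |
|---|---|---|---|
| Tear, 4% vs 6% | both arms | 3.39% vs 5.10% | −1.71 (risk ratio 0.665; true 0.667) |
| Tear, 4% vs 6% | instrumental only | 4.00% vs 5.10% | −1.10 (risk ratio 0.784) |
| Tear, 4% vs 6% | manual only | 3.39% vs 6.00% | −2.61 (risk ratio 0.565) |
| Tear, 5% vs 5% | manual only | 4.24% vs 5.00% | −0.76 |
| Tear, 5% vs 5% | instrumental only | 5.00% vs 4.24% | +0.76 |
| Caesarean, 18.5% vs 15% | both arms | 16.05% vs 12.94% | +3.11 |
| Caesarean, 18.5% vs 15% | manual only | 16.05% vs 15.00% | +1.05 |
| Caesarean, 18.5% vs 15% | instrumental only | 18.50% vs 12.94% | +5.56 |

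For scale: in the second row, superiority power is about 46%. In the two caesarean rows where the true difference of 3.5 points (exactly the margin) appears smaller, the chance of wrongly declaring non-inferiority is about 6% (both arms) and 66% (manual only), against a nominal 2.5%. Which row applies, if any, cannot be read from the protocol.

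**The case against.** Several objections have force.

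- A reader might infer that 5.3 places these women in the co-primary analyses and 9.2 takes them out. The text does not go that far: the only purpose given in 5.3 is safety monitoring. The explicit conflict is about collecting and uploading data; use in the primary analysis is not stated anywhere. This stands, and the correction has to settle it.
- A reader might infer that the trial becomes underpowered. It does not: superiority power at 5% loss is 0.3 points below its value at the planned 4% loss, and non-inferiority power stays above 90% throughout the range shown.
- A reader might infer a known bias towards manual rotation. Nothing in the protocol fixes the direction. Section 5.2 reports community fear of forceps which, if it drove refusal, would point more to the instrumental arm and so to a diluted tear benefit. Equal excess refusal in both arms leaves the risk ratio for tears almost unchanged.
- A reader might take the pilot table as accepting 5-10% without written consent. Under 8.1.2, amber calls for adapting the protocol, so it is not an accepted loss.
- Section 5.4 covers a situation that it calls rare. It gives a confidentiality reason and names a possible Section 251 application for future participants. It is a considered rule, though it still differs from 5.3.
- Section 14.2.5 acknowledges bias from missing primary outcomes and promises sensitivity analyses, with details left to the SAP. That helps with interpretation, but no analysis can recover outcomes that were barred from the database.

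**Conclusion.** The point holds as an internal contradiction with a consequence for the analysis population. Sections 5.3 and 9.1 on one side, and 9.2 (with 5.4 for non-responders) on the other, give incompatible instructions for the same randomised women. Following 9.2 or 5.4 makes inclusion in both co-primary analyses depend on something that happens after outcome and allocation are known, which is at odds with 14.2.

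The loss of power is minor. The bias could be negligible, could create a spurious tear difference of about 0.8 points, or could dilute a true 2-point benefit to about 1.1 points. Those sizes rest wholly on the assumed 20% and 5% non-consent rates and on the arm in which the excess falls. The contradiction itself needs no assumption. It must be resolved in the protocol, because it governs which data are collected.

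**What to change.** Adopt one rule throughout, subject to ethics and confidentiality approval, including the Section 251 route named in 5.4 if it is needed.

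1. Keep anonymised Day 0, 48-hour and neonatal CRF data for all randomised women without written consent.
2. State in 5.3 and 14.2 that these data enter the intention-to-treat analysis of both co-primary outcomes and the neonatal composite, as well as safety monitoring.
3. Amend the last two paragraphs of 9.2 and the 28-day rule in 5.4 to match.
4. Exempt women who explicitly ask that none of their data be used, the fourth type of discontinuation in 9.2.

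If retention is not approved, correct 5.3 and the 9.1 footnote instead. Also withdraw the 14.1 statement that caesarean loss is negligible because mode of delivery is in hospital notes, since 9.2 would leave the data in those notes and bar their use.

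The cost is protocol and participant-information wording, an ethics amendment and possibly a Section 251 application. No new data item is needed: both co-primary outcomes are already on the Day 0 CRF.

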9.3. Changes in Levels of Participation

Participants found to be ineligible post randomisation should be followed up according to all trial processes and will still have their data analysed unless they explicitly change their level of participation

Any participant who would no longer like to receive their allocated trial intervention, but is willing to be followed up in accordance with the schedule of assessments and if applicable using any central UK NHS bodies for long-term outcomes (i.e. the participant has agreed that data can be collected and used in the trial analysis) will be documented and followed-up separately.

10. ADVERSE EVENT REPORTING

10.1. Definitions

Severity Definitions	Mild Moderate	Awareness of signs or symptoms that do not interfere with the participant's usual activity or are transient and resolved without treatment and with no sequelae. A sign or symptom, which interferes with the participant's usual activity.	
	Severe	Incapacity with inability to do work or perform usual activities.	
Adverse Event	AE	Any untoward medical occurrence in a participant participating in the trial which does not necessarily have a causal relationship with the intervention received.	
Related Event	RE	An event which resulted from the administration of any of the research procedures.	
Serious Adverse Event	SAE	 An untoward occurrence that: Results in death Is life-threatening* Requires hospitalisation or prolongation of existing hospitalisation Results in persistent or significant disability or incapacity Consists of a congenital anomaly/ birth defect Or is otherwise considered medically significant by the Investigator** 	
Unexpected Event	UE	The type of event that is not listed in the protocol as an expected occurrence.	
Related and Unexpected Serious Adverse Event	N/A	A SAE that meets both the definition of a Related and Unexpected Event.	

* The term life-threatening is defined as diseases or conditions where the likelihood of death is high unless the course of the disease is interrupted.

** Medical events that may not be immediately life-threatening or result in death or hospitalisation but may jeopardise the patient or may require intervention to prevent one of the other outcomes listed in the definitions above.

10.2. Adverse Event Recording – General

The recording and reporting of Adverse Events (AEs) will be in accordance with the UK Policy Framework for Health and Social Care Research (2017), the Principles of GCP as set out in the UK Statutory Instrument (2004/1031; and subsequent amendments) and the requirements of the Health Research Authority (HRA)

Definitions for adverse event reporting are listed in table of definitions in section 10.1.

The local investigators will record AEs in the participant's medical notes and include the documentation of the assessment of severity and seriousness and also relatedness to the intervention(s) in accordance with the protocol.

